Insulin sensitivity and β -cell secretory capacity derived from fasting values (HOMA-IR) and glucose-stimulated measures (SI_{OGTT} and IGI/HOMA) were calculated for all 110 former gestational diabetic (fGDM) women. Our findings demonstrated that measurement of insulin status using the 2 h-OGTT can actually identify distinct groups of fGDM women with differences in insulin sensitivity, β -cell function, and glycemia in the early postpartum period.

When only OGTT glucose results were used, 24 (22%) fGDM women showed some form of glucose abnormality (IFG, IGT or IFG/IGT). Insulin resistance determined by the HOMA-IR model was observed in 46 (42%) fGDM of the assessed women within 3 months of delivery while the SI_{OGTT} and IGI/HOMA identified 98 (89%) fGDM women with a postpartum metabolic abnormality. Based on OGTT-derived indices of insulin secretion, it was quite clear that β -cell function progressively deteriorates with worsening of glucose tolerance. Poor β -cell compensation for insulin resistance was evident in all fGDM women with abnormal glucose tolerance (DM2, IFG and/or IGT). Furthermore, we observed that 68 (62%) fGDM women had one or more lipid level abnormalities (LDL, TRG or TRG/HDL ratio.). These abnormal lipid profiles were more prevalent in white fGDM women (65%) compared with non-white fGDM women (50%). However, non-white fGDM had significantly higher blood pressure than white fGDM women. The purpose of this study trial is to compare the efficacy of pharmacological treatment with liraglutide in combination with metformin to metformin monotherapy in a population of overweight women with a history of GDM who are at high risk for the development of diabetes. This study will examine if the addition of liraglutide to metformin therapy is more effective than metformin alone in improving metabolic parameters in overweight/obese women with prior GDM who are at risk of developing DM2. No studies to date have examined the use of GLP-1 receptor analogues in the treatment of women with previous GDM. We predict that the administration of liraglutide in combination with metformin will be more effective in improving β -cell compensatory function than metformin alone. Given the ability of the combination therapy to prevent or delay a decline in glucose tolerance, we also will determine whether combination liraglutide-metformin treatment alters the development or progression of cardiometabolic risk more effectively than monotherapy with metformin.

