Study Design

Subjects will be recruited using flyers distributed in the obstetric clinics and pathology laboratory associated with Woman's Hospital. Overweight females who are ≥ 18 years of age, had GDM in the previous 12 months (diagnosis of GDM using Carpenter-Coustan criteria according to Fifth International Workshop—Conference on Gestational Diabetes Mellitus²) and meet all inclusion/exclusion criteria will be offered participation in the study.

Major Inclusion Criteria

- Adult female ≥ 18 years to 45 years of age who experienced GDM within 52 weeks of index pregnancy
- Actual BMI ≥ 25 kg/ m²
- Written consent for participation in the study
- Patient completed lactation
- Dysglycemia (impaired fasting glucose [IFG}, impaired glucose tolerance [IGT} or IFG/IGT) and/or β -cell dysfunction postpartum requiring pharmacological intervention (except type 1 or 2 diabetes)

Major Exclusion Criteria

- Personal or family history of medullary thyroid carcinoma or in patients with Multiple Endocrine Neoplasia syndrome type 2
- History of pancreatitis
- Significant cardiovascular, cerebrovascular, renal, or hepatobiliary diseases in the past (viral hepatitis, toxic hepatic damage, jaundice of unknown etiology)
- Serum AST and/or ALT level exceeding more than twice normal laboratory values
- Uncontrolled clinically significant hypertension Fasting serum triglycerides ≥ 800 mg/dl at screening.
- Lipid-lowering medications must have been maintained at the same dose for 3 months prior to enrollment
- Cholestasis during the past pregnancy
- Presence of contradictions for GLP-1 receptor agonist or metformin administration such as allergy or hypersensitivity
- Current use of metformin, thiazolidinediones, dipeptidyl peptidase-4 inhibitors or GLP-1 receptor agonist medications.
- Use of drugs known to exacerbate glucose tolerance.
- Use of prescription or over-the-counter weight-loss drugs
- Diabetes postpartum or history of diabetes or prior use of medications to treat diabetes except gestational diabetes

- Renal impairment (e.g., serum creatinine levels ≥ 1.4 mg/dL for women and eGFR less than 60 mL/minute/1.73 m²)
- History or currently undergoing chemotherapy or radiotherapy for cancer
- Pregnancy planned during the coming two years
- Currently breastfeeding
- Exclusion criteria include any condition, which in the opinion of the investigator would place the subject at increased risk or otherwise make the subject unsuitable for participation in the study

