demonstrate dysglycemia (IFG ,IGT or IFG/IGT) and/or β -cell dysfunction that necessitates medication added to diet and exercise intervention will be recruited for the study and thus will not be inclusive of women with diabetes postpartum. The baseline blood samples from the OGTT will also be analyzed for a lipid profile which includes total cholesterol, triglycerides, HDL and LDL cholesterol, TSH, liver enzymes, creatinine with eGFR, and quantitative β hCG levels. A negative serum pregnancy test is a prerequisite for commencing treatment.

All consented patients will come into the outpatient tower for a clinic visit. A full physical examination will be performed including measurement of body mass index (BMI), waist: hip (W: H) ratio and blood pressure (BP). The total body adiposity (total fatness), defined as the accumulation of body fat without regard to regional distribution, will be expressed as BMI and calculated as weight (kg)/ height (m)², whereas the W:H ratio is a measure of body fat distribution. Height will be measured to the nearest centimeter and weight measured by a sliding weight balance to the nearest 0.1 kg. Waist circumference will be measured at the minimum circumference between the rib cage and iliac crest (in centimeters) and hip circumference at the level of the largest circumference around the buttocks by trained clinicians using tape measures from the same manufacturer. The circumference measurements will be taken in the upright position using 15-mm width flexible metric tapes held close to the body but not tight enough to indent the skin. Cardiovascular risk will be assessed biochemically using lipoprotein profile (total cholesterol, triglycerides, HDL, calculated LDL), and by total body fat and its distribution W: H ratio.

Randomization and Allocation

At randomization, all study participants will be assigned to an 80 [+4 weeks] medication treatment group. A computer-generated randomization schedule using a block randomization method will be used. The treatment allocation ratio will be 1:1. Drug will be packaged and labeled according to the randomization schemes. Subjects who are randomized will be assigned the next sequential subject number. Once randomized, the subjects will begin treatment with the allocated study drug or placebo. All personnel involved in the study will be blinded to which treatment arm the patients have been randomized. The drug and placebo will look identical and not have any identifying characteristics.

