Oral glucose tolerance tests with glucose (G) and insulin (I) measured at 0, 30, 60, and 120 after glucose load to assess diabetes, insulin resistance and pancreatic β -cell function will be performed 32 (+4) weeks after study medications are started. Testing will be repeated at 56 (+4) weeks and 80 (+4) weeks after treatment start. The baseline blood samples from the OGTT will also be analyzed for liver enzymes, TSH, creatinine with eGFR (baseline and 56 weeks only), and lipid profile. Subjects will remain on treatment unless they are diagnosed with DM2 during an OGTT or a random blood test at which time final testing will be performed. They will be withdrawn from the study and they will be referred to a specialist for additional treatment of

diabetes. In subjects who complete 80 (+4) weeks of treatment, all study medications will be stopped and subjects will be asked to return for routine OGTT testing by their physician.

Primary Study Endpoint:

- An index of *insulin secretion in relation to insulin resistance (IS-SI)* will be calculated. Thus, β -cell compensatory capacity will be evaluated by the insulin sensitivity-secretion index (IS-SI) defined as the product of composite insulin sensitivity index and first-phase insulin release index (insulinogenic index).

Secondary Study Endpoint(s):

- Indexes of insulin sensitivity and secretion using the serum glucose and insulin concentrations obtained in the fasting state and during the 2hr OGTT with INS will be computed by several measures previously validated in women. Changes in insulin resistance –baseline {HOMA-IR} and composite insulin sensitivity index [ISI_{OGTT}], and pancreatic β -cell function (corrected insulin response [CIR_{glupeak}] and insulinogenic index [IGI])/HOMA-IR
- Anthropometric measurements [BMI, absolute body weight, waist circumference, waist: hip ratio,
- Cardiometabolic risk measures [lipids, liver enzymes; blood pressure]
- Development of diabetes, impaired glucose tolerance or impaired fasting glucose based on positive OGTT. Glucose tolerance will be defined as normal, impaired glucose tolerance (IGT) or diabetic according to the criteria of the American Diabetes Association.¹ Patients diagnosed with diabetes will be withdrawn from the study and referred to a specialized physician.

Biochemical assays and calculations

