The primary outcome measure is the insulin sensitivity-secretion index (IS-SI) and secondary outcome measures include changes in lipid and hepatic enzyme levels, anthropometric parameters, insulin sensitivity and pancreatic β -cell function, and glucose tolerance status. Continuous variables will be tested for normality of distribution using the Kolmogorov-Smirnov test. Natural log transformations of skewed variables will be used where necessary in subsequent analyses. For variables with highly skewed distributions, a logarithmic transformation will be done first and the geometric means reported instead. Differences in effects of drug intervention for continuous variables (in their raw or transformed state) will be compared using Subjects/Drug Treatments by trials analyses of variance (ANOVAs). This analysis provides p values for differences between groups/drug treatments (A), differences over time (B), and the interaction of group/drug treatment with time (AB). Otherwise, changes between baseline and follow-up measurements will be compared between groups by Wilcoxon's nonparametric methods. Anthropometric measurements (body weight, BMI), blood pressure, direct and indirect measurements of carbohydrate metabolism (HOMA, SI_{OGTT} , CIRgp, IGI, and ISSI), and measurements of lipid profile (total cholesterol, HDL, LDL), and liver enzymes (ALT, AST) will be considered as dependent variables. The simultaneous effect of various baseline characteristics and characteristics at certain study treatment intervals between women who did not develop diabetes and women who did during follow-up will be studied with the use of a linear multiple regression analysis. Diabetes and IGT occurrence before and after different treatment will be compared with the McNemar test (complex chi square for paired data), which formally tests for a change between the observed proportions of 2 related samples.

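### Impaired fasting glucose (IFG) is an entry condition and a named secondary endpoint, but it has no place in the stated glucose-tolerance categories and no planned test

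*Combined protocol and SAP*

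**What the plan says.** IFG appears in the entry criteria and in the endpoint:

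- Major Inclusion Criteria admit women with "Dysglycemia (impaired fasting glucose [IFG}, impaired glucose tolerance [IGT} or IFG/IGT) and/or β -cell dysfunction postpartum requiring pharmacological intervention". Study Design repeats this for women who "demonstrate dysglycemia (IFG ,IGT or IFG/IGT) and/or β -cell dysfunction that necessitates medication added to diet and exercise intervention". IFG on its own is enough. It is not required, because β-cell dysfunction alone also qualifies.
- Secondary Study Endpoint(s) include "Development of diabetes, impaired glucose tolerance or impaired fasting glucose based on positive OGTT".

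IFG is missing from the rules that would put the endpoint into practice:

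- The sentence that follows the endpoint is "Glucose tolerance will be defined as normal, impaired glucose tolerance (IGT) or diabetic", by reference to American Diabetes Association criteria. Study Design uses the same sentence for the screening OGTT. Neither place gives glucose cut-offs.
- The Statistical Analysis Plan states: "Diabetes and IGT occurrence before and after different treatment will be compared with the McNemar test". It names no other test for glucose categories.

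The Rationale treats IFG as abnormal. Reporting the site's own cohort of 110 women, it says that poor β-cell compensation was "evident in all fGDM women with abnormal glucose tolerance (DM2, IFG and/or IGT"), and that on OGTT glucose alone "24 (22%) fGDM women showed some form of glucose abnormality (IFG, IGT or IFG/IGT").

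**The concern.** A named endpoint should have a category for each of its states and an analysis that uses them. Here one of the three named outcomes has neither. The analyst would have to decide, after data are in hand, whether isolated IFG is normal, abnormal or left out. That choice alters the baseline table, the count of women who develop abnormal glucose, and the direction in which some women appear to move during treatment. Women enrolled for β-cell dysfunction alone are also affected: if one of them develops isolated IFG, she has met the secondary endpoint as worded, but the specified test would not register it.

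**Working it through.** No stated sample size, power or error rate is in question here, so there is no design figure to reproduce. The check has two parts.

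**1. Follow each transition through the stated rules.** The McNemar test works on a paired yes/no for each condition, and the only conditions named are diabetes and IGT. IGT is read as distinct from IFG, as the inclusion criteria and the endpoint sentence both do.

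| Before | After | Registered by the test on diabetes and IGT? |
|---|---|---|
| Normal | Isolated IFG | No, although it is a named endpoint event |
| Isolated IFG | Normal | No |
| Isolated IFG | IGT or diabetes | Yes, as new IGT or diabetes; the starting abnormality is not recorded |
| IGT, or IFG with IGT | Isolated IFG | Yes, as loss of IGT, although the woman is still dysglycaemic |
| Isolated IFG | Isolated IFG | No; the same as normal throughout |

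The gap therefore goes beyond an untested component. In the fourth row, a woman who remains dysglycaemic contributes to the test as an improvement.

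The rest of the Statistical Analysis Plan does not fill the gap. Its carbohydrate-metabolism dependent variables are HOMA, SI_OGTT, CIRgp, IGI and ISSI. Its regression contrasts women who did and did not develop diabetes. Neither analyses IFG.

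**2. How many women could be affected?** Inputs from the Rationale: 24 of 110 with IFG, IGT or both, and 98 of 110 with a metabolic abnormality on OGTT indices. Input from Sample Size Computation and Power Analysis: 150 to be recruited.

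- Stated percentages reproduced: 24/110 = 21.8% (given as 22%) and 98/110 = 89.1% (given as 89%).
- The 24 are not divided into isolated IFG, isolated IGT and combined, so the isolated-IFG share s is unknown.
- Assumption A: enrolled women resemble the 98, and the 24 lie within them. Dysglycaemic share = 24/98 = 24.5%. Expected dysglycaemic women = 150 × 24/98 = 36.7. The isolated-IFG count is 36.7 × s:

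| s | 0% | 25% | 50% | 75% | 100% |
|---|---|---|---|---|---|
| Women of 150 | 0 | 9.2 | 18.4 | 27.6 | 36.7 |

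- Assumption B: every enrolled woman is dysglycaemic. The count is 150 × s, so 0 to 150.

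The trial also requires BMI of at least 25 kg/m², a restriction not stated for the 110, so even the 24.5% may not carry over. These counts cover women with isolated IFG at entry. New isolated IFG during treatment would add to them, and the documents give no rate for it.

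**The case against.** A reader might go further and say that women with isolated IFG are counted as normal. The documents do not say so. That reading follows only if the three listed states are exhaustive and IGT is strictly separate from IFG. The Rationale places IFG under abnormal glucose tolerance, the inclusion criteria call it dysglycaemia, and the endpoint sentence treats it as an outcome. The text equally allows such women to be left unclassified, or to be brought in through the cited American Diabetes Association criteria. This part of the objection stands: the class is undefined, and normal is only what remains by elimination.

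It may also be said that the cited criteria settle the matter. Their content cannot be checked from the documents, and the citation does not point to one place. The same sentence carries reference 34 in Study Design and reference 1 in Secondary Study Endpoint(s). By their listed titles, these are a consensus conference on insulin resistance and a position statement on gestational diabetes. The citation therefore does not tell the analyst where isolated IFG belongs.

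Three further limits stand:

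- The omission is one sentence used twice plus one test description. That is weak evidence of a deliberate exclusion.
- No normalisation rate is a defined endpoint, so it cannot be said that such a rate will be wrong.
- The Statistical Analysis Plan lists glucose tolerance status among secondary outcomes and promises percentages for categorical variables, and fasting glucose enters HOMA-IR and the OGTT sensitivity index. IFG might still be reported descriptively. What is missing is its category and its test.

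Finally, this is one secondary endpoint in a self-described pilot, and the raw glucose values are collected, so nothing is lost irretrievably. That limits the severity but does not remove the conflict between the endpoint and the rules meant to analyse it.

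**Conclusion.** The point holds as an internal inconsistency. The plan recruits on IFG and names its development as an outcome. It then gives a classification with no place for isolated IFG and a test that does not include it. Followed literally, new or resolved isolated IFG enters no planned test, and a change from IGT to isolated IFG would register only as loss of IGT.

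The size cannot be fixed from the documents. It is 0 to about 37 of 150 women at entry if enrolled women resemble the 98 with an abnormality, and up to 150 in the limiting case where all are dysglycaemic. Any narrower figure would need a split of the 24 that the documents do not give. The primary endpoint (IS-SI) and the sample size are unaffected. The point should be corrected before analysis, but it does not threaten the trial's main conclusion.

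**What to change.** In Study Design and Secondary Study Endpoint(s), replace the three-way sentence with mutually exclusive categories: normal, isolated IFG, isolated IGT, combined IFG/IGT, and diabetes. Cite one criteria source, by version and with its cut-offs, in both places.

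In the Statistical Analysis Plan, name IFG in the analysis of glucose-tolerance status. Compare between the randomised arms the proportion with any dysglycaemia (IFG, IGT or diabetes), adjusted for baseline category. State in advance whether the time point is week 80 or the last assessment. The McNemar test is a paired before-and-after test and does not by itself compare the arms, so it cannot serve as the main analysis of this endpoint. Women diagnosed with diabetes are withdrawn after final testing and may have no week-80 result; count them as events rather than as missing.

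The cost is protocol and SAP wording only. Fasting and 2-hour glucose are already measured at baseline and at weeks 32, 56 and 80, so no new data, visits or women are needed.

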Early phase insulin secretion (*insulinogenic index [IGI]*) is calculated as the ratio between serum insulin and blood glucose concentrations 30 min after the glucose load.⁴⁰ The IGI is calculated from the OGTT data as the ratio of the increment of insulin to that of glucose 30 min after a glucose load $\{ \Delta \text{insulin} (0-30 \text{ min}) \text{ in microunits per milliliter divided by the } \Delta \text{glucose} (0-30 \text{ min}) \text{ in mg per deciliter.} \}$ ⁴¹ This index has been shown previously to correlate strongly with the first phase of insulin response following an intravenous glucose tolerance test.⁴² Pancreatic β -cell function [$IGI/HOMA-IR$] is best estimated by the acute insulin response to glucose corrected for by the relative insulin resistance.⁴³

To evaluate beta cell function in relation to insulin sensitivity, an *insulin secretion-sensitivity index* (IS-SI) will be calculated from the product of the insulinogenic index (IGI) and the ISI_{OGTT} based on the existence of the /predicted hyperbolic relationship between these two measures.⁴⁴ Based on this relationship of insulin sensitivity and insulin secretion, changes in insulin secretion may reflect one of three scenarios regarding β -cell function. No change in the relationship would result in β -cell function moving along the curve. The second would be one in which β -cell function was improved; this would be characterized by a change in the relationship between insulin sensitivity and the insulin response with a shift to the right of or above the curve. Finally, a decrease in β -cell function would be characterized by a shift to the left of or below the curve. The insulin secretion/insulin resistance (disposition) index calculated as the product of insulin secretion measured with $(\Delta I_{0-30} / \Delta G_{0-30})$ and ISI_{OGTT} has been shown to have excellent power to predict onset of type 2 diabetes.⁴⁵

Concomitant Medications and Therapy:

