The reason for a subject discontinuing from the study will be recorded in the patient chart. A discontinuation occurs when an enrolled subject ceases participation in the study, regardless of the circumstances, prior to completion of the protocol. The investigator must determine the primary reason for discontinuation. Withdrawal due to adverse event will be distinguished from withdrawal due to insufficient response according to the definition of adverse event noted earlier. The final evaluation required by the protocol will be performed at the time of study discontinuation. The investigator will record the reason for study discontinuation, provide or arrange for appropriate follow-up (if required) for such subjects, and document the course of the subject's condition. They will also to be reported to Woman's Hospital Foundation Institutional Review Board at [contact] and Woman's Health Research Department at [contact].

Sample Size Computation and Power Analysis

A priori sample size analysis was performed using the online calculator provided by the Massachusetts General Hospital Mallinckrodt General Clinical Research Center (http://hedwig.mgh.harvard.edu/sample_size/size.html). Because the possible advantages of combination treatment over metformin alone rely on the presumed positive effects of liraglutide on pancreatic β -cell function parameters, we used the difference in a surrogate marker of insulin secretion relative to insulin resistance as the primary outcome for sample size analysis. An experimental design including a total of 118 patients would have power above 0.80 to detect differences in the IS-SI index between treatments such as those previously reported using a similar experimental design.⁴⁶

We plan on recruiting 150 overweight women with a recent history of GDM to be studied. The estimated enrollment: of 75/group for an average follow up of 60 weeks of treatment (range 32-84 weeks) will be our intent-to-treat population. This sample size is projected to provide power ≥ 0.8 to detect a $\geq 20\%$ difference in insulin action indices between treatment groups at a median follow-up of 24 months. The calculation was adapted to allow for significant dropout rate (20-22%) for completion of the full trial of 80 (+4) weeks of treatment. Subjects who drop out of the trial will not be replaced

Statistical Analysis Plan:

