All analyses will be conducted with subjects assigned to their initial treatment group, using all available data for the period of follow-up relevant to the particular analysis. Data will be analyzed on the basis of intention to treat and also on completed treatment parameters where relevant. Differences of $P < 0.05$ will be considered statistically significant. Results will be reported as mean \pm standard error of the mean (S.E.M) for quantitative variables and percentages for categorical variables unless otherwise noted. We will perform all statistical analyses using SPSS 15.0 for Windows (SPSS, Inc.; Chicago, Ill).

Study Drugs

Description

Both active drug (Liraglutide 6.0 mg/ml injection) and placebo will be supplied by Novo Nordisk A/S. as a pre-filled pen for subcutaneous injection. Each liraglutide pre-filled pen contains 18 mg/3 ml (6 mg/ml) and will deliver 30 doses of 0.6 mg; 15 doses of 1.2 mg or 10 doses of 1.8 mg; the placebo pen will deliver equal volumes of vehicle solution only. Liraglutide and placebo are visually identical.

Metformin Hydrochloride XR (extended-release) in 500 mg strength oral tablets will be purchased in bulk through the Woman's Hospital Infusion Pharmacy. Metformin hydrochloride XR is combined with a drug release controlling polymer so that drug is released slowly from the dosage form. The medication will be allocated into appropriate patient dosage regimens by the hospital pharmacy personnel. Dosage of metformin XR will be prescribed according to standard directions and not exceeding the maximum recommended daily dose in adults of 2000 mg.

Trial Supplies

Double-blind Liraglutide or placebo

Liraglutide 6.0 mg/ml or placebo solution for injection in a 3 mL pre-filled pen will be supplied by Novo Nordisk A/S. The pre-filled pen will be provided as a pen-injector. The Investigator will provide each subject with Direction for Use for the liraglutide pen-injector at each dispensing visit.

Packaging and Labelling of Trial Products

Liraglutide and placebo will be packed and labelled by Novo Nordisk A/S and provided in non subject specific boxes. Labelling will be in accordance with Annex 13, local law and trial requirements.

Storage, Handling, Accountability and Destruction of Trial Products

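### Women diagnosed with diabetes leave the study after final testing, so later visits go missing for outcome-related reasons that the planned analysis does not handle

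*Combined protocol and SAP*

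**What the plan says.** **Withdrawal.** The rule appears twice. Secondary Study Endpoint(s) has: "Patients diagnosed with diabetes will be withdrawn from the study and referred to a specialized physician". Randomization and Allocation has: "They will be withdrawn from the study and they will be referred to a specialist". The Discontinuations section recognises one kind of stopping: "A discontinuation occurs when an enrolled subject ceases participation in the study, regardless of the circumstances, prior to completion of the protocol". No section describes a woman who is off study drug but still attending visits.

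**Measurement at diagnosis.** Subjects stay on treatment "unless they are diagnosed with DM2 during an OGTT or a random blood test at which time final testing will be performed". For discontinuation of any kind: "The final evaluation required by the protocol will be performed at the time of study discontinuation". Neither sentence says what the final tests consist of.

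**Schedule.** After baseline, the first oral glucose tolerance test (OGTT) is at week 32. Then: "Testing will be repeated at 56 (+4) weeks and 80 (+4) weeks after treatment start".

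**Analysis.** The Statistical Analysis Plan says "Data will be analyzed on the basis of intention to treat", with women kept in their assigned group and all available data used, and adds an analysis of completed treatment. Continuous outcomes go into a treatment-by-time ANOVA, or otherwise into Wilcoxon comparisons of change. It names no primary time point, no method for missing visits and no role for the final-testing value.

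**Link to the primary endpoint.** IS-SI is the insulinogenic index multiplied by the OGTT insulin sensitivity index. Of that same product, the Insulin sensitivity and secretion section says it "has been shown to have excellent power to predict onset of type 2 diabetes".

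**The concern.** A woman diagnosed at week 32 has no week-56 or week-80 value of IS-SI, weight, lipids or blood pressure. This differs from ordinary dropout, because what removes her is the glycaemic decline that the primary index is meant to track. If liraglutide works as the protocol predicts, the metformin-plus-placebo arm loses more of its low values, its mean among remaining women rises, and the observed difference shrinks. The completed-treatment analysis leaves these women out by construction. A conventional repeated-measures ANOVA would do the same to the main analysis, despite the intention-to-treat statement.

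The final test limits the damage only if it yields an IS-SI and that value is used. IS-SI needs insulin and glucose at several OGTT times, and a diagnosis may come from a random blood test.

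**Working it through.** **1. The plan's own figure.** The plan gives no figure for diabetes withdrawals. The nearest is its dropout allowance of 20-22%, applied to 118 women. The formula N/(1 - d) gives 118/0.80 = 147.5, 118/0.79 = 149.4 and 118/0.78 = 151.3. The planned 150 implies d = 1 - 118/150 = 21.3%, so it reproduces. The text does not say whether diabetes withdrawals are inside this allowance.

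**2. How many women could lose week 80.** A woman diagnosed at the week-80 OGTT loses no scheduled visit, so the count stops at week 56. The annual rates are those in Study Background and Rationale for women with prior GDM: troglitazone 5.4% versus placebo 12.1%, and pioglitazone 4.6% versus placebo 13.1%. With p = 1 - exp(-rate x 56/52.18):

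| Annual rate | p by week 56 | Women of 75 |
|---|---|---|
| 12.1% | 12.2% | 9.1 |
| 13.1% | 13.1% | 9.8 |
| 5.4% | 5.6% | 4.2 |
| 4.6% | 4.8% | 3.6 |

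Compounding annually instead, 1 - (1 - rate)^(56/52), gives 9.7-10.5 control and 3.7-4.4 active women.

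**3. Effect on a week-80 comparison of women still in the study.** Assumptions not in the documents:
- log IS-SI is normal with SD s = 0.5-0.7;
- the true ratio is 1.20 (log 0.1823);
- a woman is withdrawn if a risk score, correlated rho = 0.5-0.7 with log IS-SI, falls in the lowest fraction p of her arm.

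Removing the fraction p raises the mean of the rest by rho x s x L(p), where L(p) = phi(z_p)/(1 - p). Therefore:

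apparent log ratio = 0.1823 - rho x s x [L(p control) - L(p active)]

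The product rho x s runs from 0.5 x 0.5 = 0.25 to 0.7 x 0.7 = 0.49.

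| Withdrawn, control vs active | Difference in L | Ratio at 0.25 | Ratio at 0.49 |
|---|---|---|---|
| 12.2% vs 5.6% | 0.2305 - 0.1203 = 0.110 | exp(0.155) = 1.17 | exp(0.128) = 1.14 |
| 13.1% vs 4.8% | 0.2447 - 0.1052 = 0.140 | exp(0.147) = 1.16 | exp(0.114) = 1.12 |
| 7% vs 3% (smaller gap) | 0.074 | exp(0.164) = 1.18 | exp(0.146) = 1.16 |

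The share of the log effect kept is about 62-85% in the first two rows and 80-90% in the third.

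**4. Does the analysis method matter?** A separate simulation followed log IS-SI through baseline and weeks 32, 56 and 80. A woman was withdrawn after a visit at which her value fell below a threshold, set so that 5-20% of controls had left by week 56. The correlation parameter was 0.4-0.7. The true difference was the one that 59 per arm detects with 80% power at two-sided 5% (sidedness is not stated in the plan): (1.960 + 0.842) x sqrt(2/59) = 0.516 SD.

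| Week-80 analysis | Difference (SD) |
|---|---|
| Full data, nobody withdrawn | 0.51-0.52 |
| Women still in the study | 0.375-0.479 |
| Last value, including diagnosis, carried forward | 0.53-0.60 |
| Missing-at-random model on all observed visits | 0.51-0.52 |

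The second row is 7-27% below 0.516. Carrying the last value forward overshoots. The model is close to the full-data value, but in this set-up the value that triggers withdrawal is always observed.

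**The case against.** The strongest defence is that the plan already asks for the key measurement. Final testing takes place at diagnosis. Where a scheduled OGTT makes the diagnosis, that test itself supplies the insulin and glucose for IS-SI. Women stay in their assigned group with all available data. The sample size section describes an intention-to-treat population followed for 32-84 weeks, so reaching week 80 is not a condition of inclusion. Withdrawal is then driven largely by recorded data, and step 4 shows that a suitable model can work well in that case.

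Much of this stands, and it rules out three stronger readings. A reader might infer that the intention-to-treat analysis cannot be delivered at all, but a method using every observed visit could include each woman with a post-baseline value. A reader might infer that no model could repair the loss; step 4 contradicts that when the diagnosis value is observed. A reader might also infer that the worst IS-SI values are never measured, whereas the protocol requires testing at that moment.

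The inputs are also open to challenge. The rates compare thiazolidinediones with placebo, whereas both arms here receive metformin and women with postpartum diabetes are excluded. Post-diagnosis values will include the effect of other diabetes treatment, which can itself dilute the contrast.

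The defence does not show that the plan uses the model that works. It specifies an ANOVA with no missing-data method, does not assure an IS-SI when a random blood test makes the diagnosis, and gives the final value no place in the analysis.

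**Conclusion.** The point holds in a limited form. Study-level withdrawal at diabetes makes later visits missing for reasons tied to the primary endpoint, and the planned ANOVA would conventionally discard these women. A week-80 comparison of those remaining would be biased towards no effect if liraglutide is beneficial. On the illustrative inputs, a true ratio of 1.20 would appear as 1.12-1.17, or 1.16-1.18 with the smaller gap. These figures rest on an assumed SD and correlation and on borrowed rates, which may be lower on metformin. They apply to a comparison of women still in the study, which the plan does not name as primary.

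Counting every diagnosis over 80 weeks would suggest a larger loss, but women diagnosed at week 80 keep their week-80 value. What cannot be estimated without untestable assumptions is the week-80 difference in all randomised women regardless of diabetes diagnosis.

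**What to change.** 1. In Randomization and Allocation, Secondary Study Endpoint(s) and Discontinuations, separate stopping study medication from leaving the study for women diagnosed with diabetes. With consent, and where the treating physician agrees, they attend their remaining scheduled visits (weeks 56 and 80 for a woman diagnosed at week 32) for the existing measurements. Record any new diabetes treatment and its start date. Clinical referral and the stopping of treatment stay as written. Limit this to the diabetes case: a general rule would also take in stops for pregnancy and ordinary dropout, which raise separate questions.
2. State that final testing at diagnosis includes the samples needed for IS-SI where feasible, and that this value enters the intention-to-treat analysis.
3. In the Statistical Analysis Plan, analyse IS-SI with a likelihood-based repeated-measures model on all observed visits, in place of an ANOVA that drops women with a missing visit. Report results with and without post-diagnosis values.

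The cost is a protocol amendment, consent wording and some extra attendance at visits already on the schedule: on the rates above, about 13 women (9.1 + 4.2, or 9.8 + 3.6). The drawback is that later values include the effect of other treatment, which is why both sets of results should be shown.
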